
2. To further characterize and describe the proportion of participants in the Simultaneous and Sequential groups with local or systemic reactogenicity events of greater severity following each vaccination visit and cumulatively
	
2a. The proportion of participants reporting at least one moderate or greater or at least one severe or greater solicited local or systemic reactogenicity event in each vaccination group within 1-7 days following the first vaccination during which participants receive either IIV4 or placebo with an mRNA COVID-19 vaccine
 
2b. The proportion of participants reporting at least one moderate or greater or at least one severe or greater solicited local or systemic reactogenicity event in each vaccination group within 1-7 days following the second vaccination visit which participants receive either IIV4 or placebo
 
2c. The proportion of participants reporting at least one moderate or greater or at least one severe or greater solicited local or systemic reactogenicity event in each vaccination group within 1-7 days following the third vaccination visit during which all participants receive an mRNA COVID-19 vaccine alone for those receiving two doses of mRNA COVID-19 vaccine
 
2d. The proportion of participants reporting at least one moderate or greater or at least one severe or greater solicited local or systemic reactogenicity event in each vaccination group within 1-7 days following all vaccination visits combined

3. To describe the proportion of participants in Simultaneous and Sequential groups experiencing at least one unsolicited adverse event and one adverse event of special interest and to characterize these events	
3a. The proportion of participants in each vaccination group with an unsolicited adverse event occurring during the 7 days post each vaccination visit according to severity and system organ classification
 
3b. The proportion of participants in each vaccination group with an adverse event of special interest occurring during the study period according to event type

4. To compare the change of health-related quality of life (HRQOL) from baseline in the Simultaneous versus Sequential groups following the Vaccination Visit 1	4a. Comparison between vaccination groups of the mean maximal change in score from baseline on the EuroQOL 5 dimensions-5 level (EQ-5D-5L) and EuroQOL visual analogue scale (EQ VAS) within 1-7 days following the first vaccination visit

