The alternative hypothesis is the Simultaneous group is noninferior to the Sequential group in regards to the proportion of participants with at least one moderate or severe fever, chills, myalgia, or arthralgia event after visits 1 and 2.

Ha: Simultaneous group - Sequential group < 0.10 (10%)

The upper bound of a site-stratified Newcombe binomial confidence interval (Yan and Su 2010) with Cochran-Mantel-Haenszel (CMH) weighting of the difference will be used to make these assessments with no adjustment to the alpha level for multiple comparisons.

7.1.4 Secondary Objective 1

- To compare the proportion of participants with moderate or more severe fever, chills, myalgia, or arthralgia in the Simultaneous versus the Sequential Group following the first vaccination visit

7.1.5 Secondary Objective 2

- To compare the proportion of participants with moderate or more severe fever, chills, myalgia, or arthralgia in the Simultaneous versus Sequential Group following the second vaccination visit

Secondary objectives 1 and 2 will be evaluated using a Mantel-Haenszel statistic in a stratified analysis by site at the alpha 0.05 level. No adjustments will be made to the alpha level for these evaluations.

7.1.6 Secondary Objective 3

- To describe the proportions of participants in the Simultaneous and Sequential vaccination groups with solicited local and systemic reactogenicity events according to severity grade after the first and second vaccination visit and third vaccination visit for those receiving two doses of mRNA COVID-19 vaccine

Tables (one for each visit 1, 2, and 3) will be produced that summarize each solicited local and systemic reactogenicity event by classification (none, mild, moderate, and severe), as well as by moderate or severe for each study group. These tables will have the number and percentage for each classification by study group and the confidence interval of the difference between the study groups.

7.1.7 Secondary Objective 4

- To describe the proportions of participants in the Simultaneous and Sequential vaccination groups experiencing at least one serious adverse event and a description of these events

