#### 3.3 Exploratory

- a) EOM1a: Comparison of the proportion of participants reporting at least one solicited reactogenicity event to include fever, chills, myalgia, or arthralgia of moderate or greater severity in the Simultaneous group with the Sequential group within 1-7 days following Vaccination Visit 3 during which all participants receive an mRNA COVID-19 vaccine alone for those receiving two doses of mRNA COVID-19 vaccine.
- b) EOM2a. The proportion of participants reporting at least one moderate or greater or at least one severe or greater solicited local or systemic reactogenicity event in each

vaccination group within 1-7 days following the first vaccination during which participants receive either IIV4 or placebo with an mRNA COVID-19 vaccine.

EOM2b: The proportion of participants reporting at least one moderate or greater or at least one severe or greater solicited local or systemic reactogenicity event in each vaccination group within 1-7 days following the second vaccination visit which participants receive either IIV4 or placebo.

EOM2c: The proportion of participants reporting at least one moderate or greater or at least one severe or greater solicited local or systemic reactogenicity event in each vaccination group within 1-7 days following the third vaccination visit during which all participants receive an mRNA COVID-19 vaccine alone for those receiving two doses of mRNA COVID-19 vaccine.

EOM2d: The proportion of participants reporting at least one moderate or greater or at least one severe or greater solicited local or systemic reactogenicity event in each vaccination group within 1-7 days following all vaccination visits combined.

c) EOM3a: The proportion of participants in each vaccination group with an unsolicited adverse event occurring during the 7 days post each vaccination visit according to severity and system organ classification.

EOM3b: The proportion of participants in each vaccination group with an adverse event of special interest occurring during the study period according to event type.

d) EOM4a: Comparison between vaccination groups of the mean maximal change in score from baseline on the EuroQOL 5 dimensions-5 level (EQ-5D-5L) and EuroQOL visual analogue scale (EQ VAS) within 1-7 days following the first vaccination visit.

e) EOM5a: To compare secondary outcomes 3a, 3b, 3c and 4a according to baseline COVID-19 serostatus.

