## 8.2 Secondary Objectives

1. SO1: To compare the proportion of participants with moderate or more severe fever, chills, myalgia, or arthralgia in the Simultaneous versus the Sequential Group following the first vaccination visit.

This proportion will be compared between the Simultaneous versus the Sequential Group using an exact Mantel-Haenszel statistic (calculated in Proc Logistic in SAS) in a stratified analysis by site to control for the randomization blocks at the two-sided alpha 0.05 level. The site adjusted odds ratio and corresponding 95% confidence interval for the proportion of participants with moderate or more severe fever, chills, myalgia, or arthralgia following the first vaccination visit will also be calculated.

2. SO2: To compare the proportion of participants with moderate or more severe fever, chills, myalgia, or arthralgia in the Simultaneous versus Sequential Group following the second vaccination visit.

These proportions will be compared between the Simultaneous versus the Sequential Group using an exact Mantel-Haenszel statistic (calculated in Proc Logistic in SAS) in a stratified analysis by site to control for the randomization blocks at the two-sided alpha 0.05 level. The site adjusted odds ratio and corresponding 95% confidence interval for the proportion of participants with moderate or more severe fever, chills, myalgia, or arthralgia following the second vaccination visit will also be calculated.

3. SO3: To describe the proportions of participants in the Simultaneous and Sequential vaccination groups with solicited local and systemic reactogenicity events according to severity grade after the first and second vaccination visit and third vaccination visit for those receiving two doses of mRNA COVID-19 vaccine.

Tables (one for each visit 1, 2, and 3) will be produced that summarize each solicited local and systemic reactogenicity event by classification (grades 1-4 as well as grades 2- 4 combined), for each vaccination group. These tables will have the number and percentage for each classification by vaccination group and the 95% confidence interval of the difference between the vaccination groups for the percentage of grades 3 and 4 combined.

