### 8.3 Exploratory Objectives

1. EO1: To compare the proportion of participants with moderate or more severe fever, chills, myalgia, or arthralgia in the Simultaneous versus Sequential Group following the third vaccination visit for those receiving two doses of mRNA COVID-19 vaccine.

This proportion will be compared between the Simultaneous versus the Sequential Group using an exact Mantel-Haenszel statistic (calculated in Proc Logistic in SAS) in a stratified analysis by site to control for the randomization blocks at the two-sided alpha 0.05 level. The site adjusted odds ratio and corresponding 95% confidence interval for the proportion of participants with moderate or more severe fever, chills, myalgia, or arthralgia following the first vaccination visit will also be calculated.

2. EO2: To further characterize and describe the proportion of participants in the Simultaneous and Sequential groups with local or systemic reactogenicity events of greater severity following each vaccination visit and cumulatively.

Tables for each visit 1, 2, and 3, as well as a combined visit table, will be produced that summarize the number of participants by vaccination group with at least one grade 1 or higher local or systemic reactogenicity event, as well as the number of participants by vaccination group with at least one grade 3 or higher local or systemic reactogenicity event. This table will have the number and percentage for each outcome by vaccination group and the 95% confidence interval of the difference between the vaccination groups will be presented.

3. EO3: To describe the proportion of participants in Simultaneous and Sequential groups experiencing at least one unsolicited adverse event and one adverse event of special interest and to characterize these events.

Tables will be produced that summarize participants experiencing at least one unsolicited adverse event and summarize participants experiencing at least one adverse event of special interest during the study period by vaccination group. These tables will have the number and percentage of participants experiencing either outcome by vaccination group and the 95% confidence interval of the difference between the vaccination groups. Listings with the clinical narratives will also be provided. The primary analysis population will be the Full Analysis Population 2.

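### SAP 8.3 tabulates EO2 at grade 1 or higher although the predefined outcome starts at grade 2; EO1's odds ratio names the wrong visit, and SO3's interval is narrower than Protocol 7.1.6

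*SAP*

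**What the plan says.** **EO2.** The outcome definitions EOM2a-d in SAP 3.3 count participants "reporting at least one moderate or greater or at least one severe or greater solicited local or systemic reactogenicity event", after each of three visits and over all visits combined. Protocol section 2, exploratory outcomes 2a-2d, defines the same outcome. SAP Tables 1 and 2 equate mild with grade 1, moderate with grade 2 and severe with grade 3. The analysis text in SAP 8.3 uses a different lower cut. It tabulates participants "with at least one grade 1 or higher local or systemic reactogenicity event", together with participants "with at least one grade 3 or higher local or systemic reactogenicity event".

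**EO1.** The objective and EOM1a (SAP 3.3) concern Visit 3, in participants given two COVID-19 vaccine doses. SAP 8.3 specifies an exact Mantel-Haenszel test of that proportion, then an odds ratio and 95% interval for the composite "following the first vaccination visit will also be calculated".

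**SO3.** SAP 8.2 lists counts and percentages for grades 1-4 and for grades 2-4 combined, and then gives "the 95% confidence interval of the difference between the vaccination groups for the percentage of grades 3 and 4 combined". Protocol 7.1.6 lists none, mild, moderate, severe, and a combined moderate-or-severe class, and says: "These tables will have the number and percentage for each classification by study group and the confidence interval of the difference between the study groups".

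**The concern.** SAP 8 is the text from which tables are programmed. Protocol 7.1.8 leaves the exploratory analyses entirely to the SAP, and the SAP is final (version 1.0), so for EO1 and EO2 no other method text would correct an error.

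EO2 exists to describe reactions of greater severity. A grade 1+ count measures any reaction at all and says nothing about how many participants had a moderate one. EO1 would have a p-value for Visit 3 but no effect size for that visit. SO3 would show the grades 2-4 percentages for each symptom without an interval for the group difference. SAP 8.3 applies the SO3 methods again in EO5 (serostatus) and EO6 (product), so the restriction carries into those comparisons.

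**Working it through.** **1. The plan's power figure, to confirm that it is not involved.** Inputs from SAP 4.3: 15% in each group, margin 0.10, 214 per group, one-sided alpha 0.025. Power = Φ(0.10 / √(2 × 0.15 × 0.85 / 214) − 1.96) = Φ(0.10 / 0.0345 − 1.96) = 0.826, which matches the stated 82.6%. None of the three items enters this calculation.

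**2. Definition against analysis text.**

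| Item | Predefined or protocol text | SAP 8 analysis text | Result |
|---|---|---|---|
| EO2, lower cut | grade 2+ | grade 1+ | mismatch |
| EO2, upper cut | grade 3+ | grade 3+ | agrees |
| EO1, test | Visit 3 | Visit 3 (the proportion named in the objective) | agrees |
| EO1, odds ratio and interval | Visit 3 | Visit 1 | mismatch |
| SO3, proportions | any severity and by grade (SOM3a-c) | grades 1-4, and 2-4 combined | reported |
| SO3, interval | no limit on class (Protocol 7.1.6) | grades 3-4 combined only | narrower than the protocol |

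**3. Can the missing EO2 result be recovered from another table?** The primary endpoint and SO1-SO2 cover four systemic symptoms only. EO2 covers every solicited local and systemic event. SO3 gives grades 2-4 for each event separately, but the share of participants with at least one such event lies anywhere between the largest single rate and the sum of the rates. As an illustration, take the moderate-or-worse Dose 1 rates for BNT162b2 in Protocol Table 3: fever 1.0%, chills 4.0%, muscle pain 10.1%, joint pain 4.5%. The sum is 1.0 + 4.0 + 10.1 + 4.5 = 19.6%, so even this four-symptom composite is known only to lie between 10.1% and 19.6%. The EO2 proportion cannot be rebuilt from the planned tables.

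**4. Can grade 1+ stand in for grade 2+?** Protocol Table 3, Dose 1, any grade divided by moderate or worse:

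| Symptom | BNT162b2 | mRNA-1273 |
|---|---|---|
| Fever | 3.7 / 1.0 = 3.7 | 0.9 / 0.4 = 2.3 |
| Chills | 14.0 / 4.0 = 3.5 | 9.2 / 2.3 = 4.0 |
| Muscle pain | 21.3 / 10.1 = 2.1 | 23.7 / 7.2 = 3.3 |
| Joint pain | 11.0 / 4.5 = 2.4 | 16.6 / 4.7 = 3.5 |

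It cannot. The two cuts differ by a factor of 2.1 to 4.0, and the factor varies by symptom and product.

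**5. How much can an SO3 interval on grades 3-4 show?** Severe rates for chills, muscle pain and joint pain in Table 3 run from 0.1% to 0.6%. Per arm that is 214 × 0.001 = 0.2 to 214 × 0.006 = 1.3 expected participants for each symptom, all after a first dose. After Dose 2 of BNT162b2, Protocol 1.1 gives severe fatigue as 3.8% and severe headache as 2.0%, or 214 × 0.038 = 8.1 and 214 × 0.020 = 4.3 participants. The yield of a grades 3-4 interval therefore depends on dose and symptom.

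**The case against.** The best defence is that little is lost. EO2 still reports the severe half correctly. EO1 still makes its predefined comparison at Visit 3; the odds-ratio sentence repeats SO1's and looks like a copying slip. SO3's outcomes are descriptive proportions with no interval in their definition, and those proportions are still tabulated. Protocol section 7 calls itself a summary to be completed by the SAP, and 7.1.6 does not say which classes must carry an interval. These points stand. They make EO1 and SO3 minor, and they leave the sponsor free to justify the SO3 restriction instead of lifting it. They do not restore the missing grade 2+ result in EO2.

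A reader might infer more than the documents support:

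- *That none of the three analyses reports its predefined outcome.* This is true only of the grade 2+ half of EO2.
- *That the grade 2+ threshold of the primary endpoint has no interval anywhere.* SAP 8.1 gives the four-symptom composite a site-stratified Newcombe interval over Visits 1 and 2, and SAP 8.2 gives site-adjusted odds ratios with 95% intervals after each visit. What SO3 lacks is an interval for each separate event at grades 2-4.
- *That a grades 3-4 interval would rest on almost no events.* The low rates are Dose 1 rates for selected symptoms. Protocol 1.2 expects most adults and many children to receive a booster, and Protocol 1.1 describes booster reactogenicity as generally similar to Dose 2. There, Grade 3 systemic events of any kind reached 15.7% in younger mRNA-1273 recipients.
- *That grade 1+ would sit near its ceiling in both arms.* The supporting figures, 83.1% and 86.9%, are injection-site pain after Dose 1 in younger adults. In the older groups they are 71.1% and 74.0%. Visit 2 involves no COVID-19 vaccine, and the documents give no rate for influenza vaccine alone.

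**Conclusion.** The EO2 discrepancy is established from the text: one of two predefined cuts is wrong in all four tables, and the correct result is not obtainable from any other planned table. That is the substance of the point. EO1 has a wrong visit in its effect-estimate sentence only. SO3 departs from Protocol 7.1.6 without explanation, in the scope of its interval only.

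All three concern exploratory or descriptive secondary analyses. Correction is worthwhile but bears on nothing in the primary non-inferiority test, its alpha or its power. The mismatches need no assumption beyond the SAP's own grading tables and the natural reading that EO1's test refers to the objective stated directly above it. The sizes quoted are Dose 1 rates in younger adults and serve only to show that the two cuts are not interchangeable; they do not predict this trial's rates.

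**What to change.** - **EO2 (SAP 8.3):** replace the lower cut with *at least one grade 2 or higher*, and keep grade 3 or higher. A grade 1+ row may stay as an addition.
- **EO1 (SAP 8.3):** specify the odds ratio and 95% interval *following the third vaccination visit*.
- **SO3 (SAP 8.2):** add the 95% interval of the difference for grades 2-4 combined, per event, in line with Protocol 7.1.6, or state why the interval is confined to grades 3-4. If grades 3-4 combined keeps an interval, list it among the tabulated classes. Confirm that the change carries through to EO5 and EO6.

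The cost is three wording corrections in a SAP amendment and the matching table shells. No new data, sample size or alpha change is needed.

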#### **EQ-5D-5L and Visual Analogue Scale (VAS)**

The EQ-5D-5L is a standardized, generic measure of health status that provides information on HRQOL and activities of daily living: mobility, self-care, usual activities, pain/discomfort and anxiety/depression (<http://www.euroqol.org/>). In addition, the instrument contains the EQ Visual Analogue Scale (EQ-VAS) which measures the respondent's self-rated health.

The EQ-VAS records the respondent's self-rated health on a 20 cm vertical, visual analogue scale with endpoints labelled 'the best health you can imagine' (100) and 'the worst health you can imagine' (0). The respondent marks an 'X' on the scale number to indicate how their health is 'today.' The minimum clinically important difference on the VAS is 8.

The changes from baseline will be assessed within vaccination group maximal change from baseline for each participant for the EQ-VAS and EQ-5D-5L. For the EQ-5D-5L the change between vaccination groups from baseline will be compared using a t-test or the Mann-Whitney U test (Wilcoxon rank-sum test) at the alpha 0.05 level. For the EQ-VAS, if the maximal change from baseline is 8 or greater, this will indicate a clinically relevant change. The vaccination group mean changes will be compared using a paired t-test or Wilcoxon signed-rank test at the alpha 0.05 level.

Participants under the age of 12 will not be included in the analysis because the validated index scoring is only for people 12 and older.

5. EO5: To assess the safety profiles in the simultaneous and sequential group participants by baseline COVID-19 serostatus (positive versus negative).

Secondary objectives 3 and 4 described above will be re-analyzed using the baseline COVID-19 serostatus as the group comparison within each treatment group. See the statistical methods above for details.

6. EO6: To assess the safety profiles in the simultaneous and sequential group participants by vaccine product (Pfizer or Moderna).

Secondary objectives 3 and 4 described above will be re-analyzed using the vaccine product as the group comparison within each treatment group. See the statistical methods above for details.

7. EO7: To assess the effect of simultaneous administration of IIV4 and COVID-19 vaccine on IIV4 immunogenicity as assessed by hemagglutination inhibition assay (HAI).

The proportion of participants in each vaccination group with a seroprotective HAI titer ( $\geq 1:40$ ) pre- and post-IIV4 immunization for each IIV4 antigen will be compared using a Mantel-Haenszel statistic in a stratified analysis by site to control for the randomization blocks at the two-sided alpha 0.05 level.

The proportion of participants in each vaccination group achieving seroconversion following IIV4 (an HAI titer  $> 1:40$  following IIV4 if the baseline titer is  $< 1:10$  or a four-fold rise in HAI titer if the baseline titer is  $> 1:10$ ) for each IIV4 antigen will be compared using a Mantel-Haenszel statistic in a stratified analysis by site to control for the randomization blocks at the two-sided alpha 0.05 level.

The geometric mean HAI titer (GMT) for each IIV4 antigen pre- and post-IIV4 in each vaccination group will be compared (within vaccine group pre versus post and between vaccination groups) using a regression model with the log transformed titer value at the two-sided alpha 0.05 level. The geometric mean fold rise (GMFR) in HAI titer for each vaccination group will be presented along with a 95% confidence interval.

The Immunogenicity Population is the primary analysis population.

8. EO8: Assessments of the serum antibody levels to SARS-CoV-2 antigens.

The proportion of participants in each vaccination group seropositive to SARS-CoV-2 variants tested prior to and following mRNA COVID-19 vaccine will be compared using a Mantel-Haenszel statistic in a stratified analysis by site to control for the randomization blocks at the two-sided alpha 0.05 level. Comparisons will be made pre- and post-vaccination for each variant tested. The definition of seropositive is as follows:

- $ID_{50}$  above Limit of Detection (LOD) at baseline
- after vaccination and seronegative at baseline,  $ID_{50}$  above LOD is considered seropositive
- after vaccination and seropositive at baseline, then an  $ID_{50}$  3-fold over baseline  $ID_{50}$  is considered seropositive.

The term  $ID_{50}$  refers to the inhibitory dilution where 50% neutralization occurs, and  $ID_{80}$  refers to the inhibitory dilution where 80% neutralization occurs.  $ID_{50}$  estimates are generally used for analysis purposes since they are in the linear part of the curve and more stable estimates.

The geometric mean  $ID_{50}$  and  $ID_{80}$  titers pre- and post-vaccination with mRNA COVID-19 will be compared (within vaccine group pre versus post and between vaccination groups) using a regression model adjusting for vaccine platform (Pfizer or Moderna) and study site with the log transformed titer geometric mean  $ID_{50}/ID_{80}$  values at the two-sided alpha 0.05 level. Should there exist a substantial difference (based on a statistical evaluation of these data) in titer values between the vaccine platforms, these proposed analysis and tables will be done within vaccine platform type (i.e., separate analyses for Pfizer or Moderna). This decision will be made with the study team once all data have been collected and are ready for analysis. Tables will be generated to present the geometric mean raw  $ID_{50}$  and  $ID_{80}$  values pre- and post-vaccination by vaccination group.

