5.5 Health-Related Quality of Life (HRQOL)

5.5.1 Generic Measures of HRQOL

HRQOL assessments will be performed for persons aged ≥ 12 years at baseline and daily for 7 days following receipt of either COVID-19 vaccine plus placebo or following COVID-19 vaccine plus influenza vaccine. Assessments will include the EQ-5D-5L and the EQ-VAS.

EQ-5D-5L

The EQ-5D is a standardized, generic measure of health status that provides information on HRQOL and activities of daily living: mobility, self-care, usual activities, pain/discomfort and anxiety/depression (<http://www.euroqol.org/>)⁴⁶. In addition, the instrument contains the EQ Visual Analogue Scale (EQ-VAS) which measures the respondent's self-rated health.

The EQ-5D-5L is the new version of the EQ-5D that increases the levels of severity from three to five to significantly increase reliability and sensitivity while maintaining feasibility and reducing ceiling effects (**Appendix A**)^{47,48}. The descriptive system comprises 5 dimensions of mobility, self-care, usual activities, pain/discomfort, anxiety /depression. For each of these dimensions, there are 5 response levels: no problems, slight problems, moderate problems, severe problems, and extreme problems. The respondent is asked to indicate his/her health state by ticking in the box against the most appropriate statement in each of the 5 dimensions. This decision results in a 1-digit number expressing the level selected for that dimension. The digits for 5 dimensions can be combined in a 5-digit number describing the respondent's health state from 11111 as best health and 55555 as worst health. These numbers are converted to a Utility Index that ranges from -0.109 (worst health) to 1.000 (best health) for US specific values. The minimum clinically important difference ranges from 0.05 to 0.1 depending on health conditions being studied. The EQ-5D-5L will be used for participants 12 years of age and older. HRQOL will not be collected for participants 5-11 years of age.

EQ-VAS

The EQ-VAS records the respondent's self-rated health on a 20 cm vertical, visual analogue scale with endpoints labelled 'the best health you can imagine' (100) and 'the worst health you can imagine' (0). The respondent marks an 'X' on the scale number to indicate how their health is 'today.' The minimum clinically important difference on the VAS is 8.

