### 4.4 Randomization

Participants will be randomized (1:1) to receive either IIV4 or saline injection by an unblinded vaccinator at Visit 1. Those receiving IIV4 at visit 1 will receive saline placebo at Visit 2 and those receiving saline placebo at Visit 1 will receive IIV4 at Visit 2. Randomization will be stratified by age (5 to < 12 years of age, 12 to < 18 years of age, 18 to <65 years of age, and ≥ 65 years of age) and receipt of either a primary two-dose series or booster dose of mRNA COVID-19 vaccine (for the ≥18 age groups) using a permuted block randomization scheme stratified by Lead and Contributing Sites. The project statistician will generate permuted block randomization schemes which will be uploaded to REDCap. The randomization schedule will not be available to the study staff, so the next randomization allocation will not be known before randomization occurs. Following confirmation of study eligibility criteria during Visit 1, participant randomization will be through REDCap with treatment allocation recorded on the unblinded vaccinator CRF. In the event that REDCap is unavailable, manual randomization will occur through the use of envelopes. The project statistician will prepare 10 envelopes per age group and vaccine series per site (total of 60 per site) that will use the same randomization strategy as the primary scheme embedded in REDCap. When an unblinded team member is informed of the age group, he/she will pull the next envelope in order. In order to capture the allocation per subject, a separate form in REDCap will be used by the unblinded personnel to add the assignment. A log will need to be kept at the site capturing these instances.

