Unsolicited adverse events (AEs) will be collected and reported for the 7 days following each vaccine visit. Adverse events of special interest (AESI) will be collected and reported during the entire study period [i.e. from enrollment through 120 days following enrollment]. Unsolicited AEs, SAEs, and AESIs will be graded as follows.

Mild (Grade 1)	Moderate (Grade 2)	Severe (Grade 3)	Potentially Life Threatening (Grade 4)
Noticeable but does not interfere with activity or measurement	Interferes with activity but did not need a medical visit or absenteeism [i.e. missing work or school]	Significant; prevents daily activity and/or resulted in medical visit and/or absenteeism [i.e. missing work or school]	Requires an ER visit or hospitalization

4. EO4: To compare the change of health-related quality of life (HRQOL) from baseline in the Simultaneous versus Sequential groups following the Vaccination Visit 1.

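### The SAP names a paired test for the EQ-VAS comparison of two independent arms, so the exploratory between-arm comparison has no usable test as written

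*SAP*

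**What the plan says.** EO4 in SAP section 8.3 is a between-arm objective: "To compare the change of health-related quality of life (HRQOL) from baseline in the Simultaneous versus Sequential groups following the Vaccination Visit 1". Its endpoint, EOM4a in SAP section 3.3, is worded the same way for both instruments: "Comparison between vaccination groups of the mean maximal change in score from baseline". Protocol section 2 gives the same outcome.

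The method paragraph under EO4 then takes four steps:

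- It opens with "The changes from baseline will be assessed within vaccination group maximal change from baseline for each participant for the EQ-VAS and EQ-5D-5L".
- It gives independent-sample tests for one instrument: "For the EQ-5D-5L the change between vaccination groups from baseline will be compared using a t-test or the Mann-Whitney U test (Wilcoxon rank-sum test").
- For the EQ-VAS it adds a threshold: "if the maximal change from baseline is 8 or greater, this will indicate a clinically relevant change".
- It closes with "The vaccination group mean changes will be compared using a paired t-test or Wilcoxon signed-rank test at the alpha 0.05 level".

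On allocation, SAP section 4.4 says: "Participants will be randomized (1:1) to receive either IIV4 or saline injection by an unblinded vaccinator at Visit 1". On timing, Protocol section 5.5.1 collects quality of life at baseline and "daily for 7 days following receipt of either COVID-19 vaccine plus placebo or following COVID-19 vaccine plus influenza vaccine". SAP section 5.2 asks for stratification by site for all objectives when applicable, and sets a two-sided 0.05 level for exploratory objectives.

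**The concern.** A paired t-test or signed-rank test works on differences within matched pairs. Here the two sets of change scores come from different people, and nothing in the design matches a Simultaneous participant to a Sequential one. The same paragraph uses a t-test or Mann-Whitney test for the EQ-5D-5L, which has the same data structure, so the SAP is inconsistent with itself.

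What is at stake is one exploratory result. A programmer following the text must depart from it, invent a pairing, or run a within-arm test that answers another question. That choice would be made with data in hand, which prespecification is meant to prevent.

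A smaller gap sits beside it. The EQ-VAS runs from 0 (worst) to 100 (best), but neither the maximal change nor the 8-point threshold has a stated direction. In a reactogenicity study the direction of interest is a fall.

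**Working it through.** The documents give no EQ-VAS standard deviation, power or number per arm, so there is no plan figure to reproduce here. The only power figure concerns the primary endpoint and plays no part.

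**1. Are there pairs?** Allocation is 1:1 by individual, without matching. IIV4 and placebo swap at Visit 2, which might suggest crossover pairs, but quality of life is measured only at baseline and in the week after Visit 1 (Protocol section 5.5.1 and Tables 5 to 7). Each participant gives one change score, in one arm. There are no pairs.

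**2. Read as a between-arm test.** With unequal arm sizes the paired test is undefined; the software returns an error. With n per arm, the two statistics are

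- two-sample: t = (x̄ − ȳ) / √[(s_x² + s_y²)/n]
- paired: t = (x̄ − ȳ) / √[(s_x² + s_y² − 2·r·s_x·s_y)/n]

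where r is the correlation created by the row order. With equal SDs the paired t equals the two-sample t divided by √(1 − r). Over random orderings r has mean 0 and SD 1/√(n − 1).

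- n = 100: SD of r = 1/√99 = 0.1005. At r = +0.1005 or −0.1005, t is multiplied by 1/√0.8995 = 1.054 or 1/√1.1005 = 0.953.
- n = 214: SD of r = 1/√213 = 0.0685. The factors are 1/√0.9315 = 1.036 and 1/√1.0685 = 0.967.

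Row order therefore typically moves t by about 3% to 5%, for no scientific reason.

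**3. Simulation of that reading.** Assumed, not in the documents: normal change scores, SD 15, true difference 0 or 4 points, the arm sizes shown, 4,000 runs each. Unequal arms were cut to the smaller size for the paired test.

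| Arm sizes | True difference | Two-sample test rejects | Paired test rejects | Two row orders disagree |
|---|---|---|---|---|
| 100/100 | 0 | 4.9% | 4.6% | 1.4% |
| 100/100 | 4 | 46.6% | 46.7% | 4.4% |
| 150/140 | 0 | 5.2% | 5.2% | 1.0% |
| 150/140 | 4 | 61.7% | 59.7% | 3.4% |
| 214/214 | 0 | 4.9% | 4.9% | 0.9% |
| 214/214 | 4 | 79.6% | 79.2% | 2.0% |
| 214/190 | 0 | 4.4% | 4.4% | 1.0% |
| 214/190 | 4 | 77.1% | 74.4% | 2.7% |

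Type I error stays near 5%. The costs are an arbitrary answer in a small share of cases, and lost participants when sizes differ (214 − 190 = 24 dropped in the last rows).

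**4. Read as a before-after test within each arm.** The hypothesis becomes zero mean change in that arm, not equal change in the two arms. The endpoint is an extreme over seven days, so noise alone shifts it. This was simulated as the largest fall over seven days, with no true change in either arm, visit-to-visit SD assumed at 2, 5 or 8 points, 100 or 214 per arm, and 500 runs each. The within-arm test rejected in 100% of runs, with average largest falls of about 2.7, 6.8 and 10.8 to 10.9 points. The two-sample test between arms rejected in 2.8% to 6.6% of runs (simulation standard error √(0.05 × 0.95/500) = about 1 percentage point).

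**5. Direction.** If change is post minus baseline, a value of 8 or more is an improvement, and a fall of 8 (that is, −8) does not meet the rule. If change is absolute, rises and falls both meet it. The text does not choose.

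**The case against.** The strongest defence is that the paragraph opens by assessing change within vaccination group, and a paired or signed-rank test suits a before-after analysis within each arm. On that reading the test is not wrong; the SAP has left out the between-arm EQ-VAS test. This is a fair reading of unclear text. It does not remove the need for a correction, because EOM4a requires a between-arm comparison of the EQ-VAS and no other section supplies one. Where this SAP wants both kinds of comparison (EO7 and EO8) it says so.

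It can also be said that the slip would show itself as soon as the arm sizes differed, and that the fitting tests stand in the same paragraph. Both statements are true and bear on severity.

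Three stronger readings are tempting, and the documents do not support them:

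- **That the false-positive rate is inflated, or that p-values swing widely.** Arbitrary pairing keeps the rate near 5%, and two orderings disagree in about 1% of null runs and 2% to 4.4% of runs with a 4-point difference. Large swings in the verdict can be shown only by choosing a dataset close to p = 0.05, and the documents give no EQ-VAS inputs from which to derive one.
- **That a responder count will mix benefit with harm.** The SAP defines no responder proportion, table or test. It says only that a change of 8 or more is clinically relevant. What stands is that the direction is missing.
- **That the analysis must be replaced by baseline-adjusted ANCOVA.** The independent-sample tests for the EQ-5D-5L are valid. ANCOVA is an optional improvement, not part of the error.

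**Conclusion.** The point holds: the EQ-VAS sentence does not provide a usable test of the between-arm comparison that EO4 and EOM4a require. Taken literally, the test cannot be run or depends on row order. Read as within-arm, it leaves the required comparison without a test. This follows from the wording and the design and needs no numerical assumption. Only the sizes in the working rest on assumed SDs, differences and arm sizes. The number with quality-of-life data is unknown because participants under 12 are excluded.

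Severity is should-fix. A reader might infer that the trial's main findings are at risk; they are not. EO4 is one of eight exploratory objectives, and no primary or secondary analysis uses the EQ-VAS. The missing direction is a clarification of the same low weight.

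**What to change.** In SAP section 8.3, EO4:

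- Compare each participant's maximal EQ-VAS change between arms with a two-sample t-test or Wilcoxon rank-sum test at two-sided 0.05, as already stated for the EQ-5D-5L, stratified or adjusted by site where applicable (SAP section 5.2).
- If a before-after test is wanted, list it separately as within-arm and descriptive.
- State the direction of maximal change for both instruments, and say that on the EQ-VAS a decrease of 8 points or more is a clinically relevant worsening.
- Optionally, add a baseline-adjusted ANCOVA as a supporting analysis.

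The cost is a few sentences in a new SAP version, with no new data. The protocol outcome also leaves the direction open, so the team should record the choice as a clarification of that outcome, ideally before the EQ-VAS data are examined by arm.
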